6.3.2 Efficacy Analysis

The primary evaluation point is overall response at 24 weeks using the NIH cGVHD response criteria measures⁵¹. The overall response score will be assessed as CR, PR, or lack of response as per NIH guidelines. The organ-specific and other subcomponents of the overall response score will be analyzed individually and absolute values recorded.

Up to 2 corticosteroid pulses will be allowed, one for initial flares and one for late flares as described in Section [4.1](#).

Response will be assessed every 12 weeks from the start of baricitinib. To ensure comparability, baseline and on-study methods for response assessment will be performed using identical grading, scale or techniques. The Chronic GVHD Assessment (Clinician) Form will be completed at each 12 week evaluation visit ([Appendix F](#)). Included in that form are both organ-specific primary measurements and clinician-assessed secondary measurements. The response of each affected organ will be evaluated and an overall response will be determined.

6.3.2.1 Response Criteria

Efficacy will be assessed using NIH consensus criteria measuring for therapeutic response in clinical trials for cGVHD.

- **CR** is defined as resolution of all manifestations in each organ or site
- **PR** is defined as improvement at least 1 organ or site without progression in any other organ or site. The criteria for PR and progression are provided in [Appendix K](#)
- **Lack of Response:** including unchanged, mixed response, and disease progression:
- **Mixed response:** CR or PR in at least 1 organ accompanied by progression in another organ
- **Disease progression:** see [Appendix K](#) for organ criteria
- **Unchanged:** Outcomes that do not meet the criteria for CR, PR, disease progression, or mixed response

As outlined in Section [3.7](#), type of involved organ, location and its measurements will be recorded at scheduled evaluations and reported on the appropriate CRF, equal to “Chronic GVHD Assessment (Clinician) Form,” ([Appendix F](#)). All other measurements not being included in primary assessment but clinically related to cGVHD (e.g., change of pigmentation) will be reported in the source documents.

Skin and skin appendages: Skin assessment will be based on the NIH 0-3 Skin Score, which correlates with cGVHD severity, symptoms, and survival ([Appendix D](#)). Clinician-perceived severity of sclerosis will also be captured on a 0-10 scale. Patient-reported symptoms will be captured on a 0-10 scale and on the Lee symptom scale.

Musculoskeletal connective tissue: Assessment of joint range of motion will be performed by the photographic range of motion (P-ROM) scale and the NIH 0-3 Joint Score, which correlate with changes in joint involvement. In a prior study, both scales performed well but the Joint/Fascia scale better reflected clinical perception of improvement, and the P-ROM better reflected the clinical perception of worsening³³. If these measurements are discrepant, priority

will be given to the NIH 0-3 scale when improvement is detected, and to P-ROM when worsening is detected. If the resolution cannot be achieved then the priority will be given to the NIH 0-3 Joint/Fascia scale, as the P-ROM is of more recent origin and still deemed exploratory in the 2014 NIH cGVHD organ staging recommendations⁴.

Eyes: The NIH Eye Score uses a scale of 0-3 based on symptoms, need for eye drops, and use of therapeutic procedures or devices. This has been shown to detect improvement of worsening in ocular cGVHD. Patient-reported symptoms will be captured on a 0-10 scale and on the Lee symptom scale.

Mouth: Mouth assessments on the NIH-modified Oral Mucosa Rating Scale (OMRS) include:

- (1) mucosal erythema by 0-3 grading based on the color intensity, (2) lichen-type hyperkeratosis by 0-3 grading based on the percentage of oral surface area, (3) ulceration by 0-6 based on percentage of oral surface area

Gastrointestinal tract: Gastrointestinal (GI) symptoms will be graded through interview by the investigator according to 0-3 severity scales, and weight will be measured at each visit.

Liver: Involvement of liver is graded according to the levels of total serum bilirubin, alkaline phosphatase, and alanine aminotransferase (ALT).

Lung: Absolute percent predicted of the forced expiratory volume in the first second (FEV1), forced vital capacity (FVC), single breath diffusion lung capacity for carbon monoxide (DLCO), total lung capacity (TLC), and residual volume (RV) will be measured on pulmonary function testing (post-bronchodilator response values, as cGVHD of the lungs is not a bronchodilator-responsive process). The %FEV1 will be used for response assessment. Symptoms will be graded through interview by the investigator according to the NIH Symptom Scale 0-3. Slope of %FEV1 will also be measured.

Genitals: Patient-reported symptoms will be captured on a 0-10 scale. **Global chronic GVHD Rating:** The overall clinical impression of patient's cGVHD will be recorded on a 4-point (0-3) scale on the Chronic GVHD Assessment (Clinician) Form.

Chronic GVHD Improvement Scale: The overall changes of patient's cGVHD symptoms during previous 3 months will be recorded on a 7-point (-3 to +3) scale on the Chronic GVHD Assessment (Clinician) Form.

Chronic GVHD Symptom Severity Scale: The overall severity of patient's cGVHD symptoms will be recorded on an 11-point (0-10) numeric scale on the Chronic GVHD Assessment (Clinician) Form.

Lee symptom scale was developed as a 30-item symptom scale with 7 subscales to capture the cGVHD-specific symptom burden (**Appendix I**). This symptom scale showed to correlate with persons' self-assessed mild, moderate, and severe cGVHD manifestations in cross-sectional validation analysis. Evidence supports the validity, reliability, and sensitivity to chronic GVHD severity.

NIH organ 0-3 scoring (Appendix D**)** will be collected at the evaluation endpoints.

6.3.2.2 Summary of Response Measures

- i. Primary response measures
 - 1. Skin: NIH 0-3 Skin Score

2. Joints: P-ROM (1-7 and 1-4) and NIH Joints Fascia Score
 3. Eye: NIH 0-3 Eye Score
 4. Mouth: NIH-modified 0-12 OMRS
 5. GI: GI 0-3 clinician symptom severity scale
 6. Liver: bilirubin, alkaline phosphatase, ALT
 7. Lung: %FEV1
 8. Clinician global assessment scale (3-point, 7-point change, 11-point)
- ii. Secondary assessments
1. Overall response rate at 12 weeks of therapy
 2. NIH organ scoring
 3. Rate of >50% reduction of immunosuppressive therapy at 24 weeks and 48 weeks (steroid pulses on study per section 4.1 will not count towards this assessment)
 4. Overall survival
 5. Platelet count, CRP, C3, C4, albumin
 6. Lee symptom scale, HAP, FACT-BMT
 7. Skin and oral biopsies (if positive at baseline)
 8. MRI (if positive baseline)
 9. Pharmacokinetics
 10. Pharmacodynamic/correlative studies

6.3.2.3 Other endpoints to be recorded at the evaluation time points: Need for secondary systemic therapy for GVHD, malignancy progression, discontinuation of immune suppression, steroid doses, other immunosuppressive drug doses, new topical treatments introduced, intensity of immunosuppression scale, NIH global severity (**Appendix E**), survival, progression-free/malignancy-free survival, disability-free survival.

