Neutrophils $< 1.0 \times 10^9/L$, platelets $< 50 \times 10^9/L$, creatinine ≥ 1.5 times the upper limit of normal **or** estimated creatinine clearance $< 50 \text{ mL/min/1.73m}^2$ (Cockcroft-Gault formula), serum aspartate aminotransferase or alanine aminotransferase concentration $> 3 \times \text{ULN}$ or total bilirubin $\geq 1.5 \times \text{ULN}$

Progressive malignancy, uncontrolled infection or any major organ dysfunction as defined by the protocol

Design:

This is a Phase 1/2 trial to determine the safety and efficacy of baricitinib in patients with cGVHD that is refractory to steroids.

Patients will initially be treated with baricitinib at 2mg daily for 12 weeks. If the response at 12 weeks is a CR and there has not been a DLT, the dose will remain at 2mg daily for an additional 12 weeks, with the primary response assessment at 24 weeks of total treatment. If the response is a PR or stable disease, the dose will be increased to 4mg daily for an additional 12 weeks, with the primary response assessment at 24 weeks of total treatment. If there is progression of disease at any time within the first 12 weeks, the dose can be increased to 4mg daily at that time, and patients will continue for a total of 24 weeks of treatment. Patients will have the option to continue baricitinib for an additional 6 months as tolerated if they have stable or responding disease.

The co-primary endpoint of safety will be determined by rate, severity, and duration of adverse events based on CTCAE v4 criteria. Assessment for DLTs will occur every 2 weeks during the first 4 weeks of each dose level. Safety monitoring will occur every 4 weeks thereafter.

The co-primary endpoint of efficacy will be defined as rate of overall response at 24 weeks per NIH consensus criteria (CR or PR).

Peripheral blood samples will be collected prior to treatment, at 2 weeks, at 12 weeks and every 12 weeks thereafter to evaluate cytokine and cellular profiles, STAT phosphorylation, candidate chronic GVHD biomarkers. Pharmacokinetic studies will also be performed at each dose level.

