3 STUDY IMPLEMENTATION

3.1 STUDY DESIGN

This is a phase 1/2 single arm study to evaluate the safety and efficacy of baricitinib at doses of 2mg-4mg in patients with cGVHD after SCT. Doses of 0.5mg-20mg have been studied in patients with autoimmune diseases and have demonstrated a good safety profile (Baricitinib Investigator's Brochure, Eli Lilly and Company). Based on studies in patients with RA, there seems to be a plateau efficacy response at doses above 4mg daily, and it is the 4mg daily dose that was taken to the Phase 3 studies. In addition, in anecdotal experience with JAK inhibitors in patients with GVHD, low doses appear to be sufficient for response.

Patients will be enrolled in up to 2 sequential cohorts of up to 21 patients.

The first cohort of patients will be treated with baricitinib starting at a dose of 2mg daily for 12 weeks. For safety purposes, patients who experience a DLT within the first 4 weeks will be able to restart at 1mg daily, and will continue at this dose as tolerated (see Section 3.1.1). If they experience a DLT at this dose, they will be taken off treatment. Regarding efficacy, patients who have a complete response (CR) on 2mg daily at 12 weeks will continue the same dose until the 24 week time point for the primary efficacy endpoint. For patients who have a partial response (PR) or unchanged disease at 12 weeks, the dose will be increased to 4mg daily until the primary efficacy endpoint response assessment at 24 weeks. Following any dose increase to 4mg, patients who experience a DLT within the first 4 weeks will have a dose reduction back to 2mg daily. For patients who experience cGVHD progression at any time within the first 12 weeks on 2mg daily, the dose can be increased to 4mg daily up until the primary efficacy endpoint response assessment at 24 weeks, unless they experience a DLT. Prior to the 12 week response assessment, an initial response assessment will occur at 6 weeks, but there will be no dose changes unless there has been progression or toxicities, as outlined. If at least 1 patient in the first cohort has a PR or CR, the remainder of the study will follow the initial schema as above, and 21 evaluable patients will be treated as part of cohort 1. After the primary response assessment, patients who have unchanged or responding disease will have the option to continue baricitinib for an additional 6 months as tolerated.

[figure not shown]
[figure not shown]

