3.5 FOLLOW-UP

All persons will be followed for adverse events for whichever is longer, 30 days after last dose of baricitinib or until return to baseline or stabilization of AE per section [6.1 0](#) by phone call.

Patients who discontinue therapy before completion of the 24 or 48 weeks will be asked to return for a follow up visit to complete their off treatment assessments within 30 days after the last dose

of study drug. Patients who discontinue therapy at the completion of 24 or 48 weeks will complete the off treatment assessments at the last scheduled visit. Following this, patients will be invited for a follow up visit at 3 months after last dose, then followed up by a phone call to the patient and/or the primary physician's office at 12, 18 and 24 months after completing baricitinib. If they choose not to follow up at 3 months, they will be followed up by phone call. The phone call will focus on a) survival status and cause of death if pertinent, b) ongoing systemic treatment for cGVHD and date of discontinuation, c) primary malignancy progression, d) any second primary malignancy, e) return to work part-time or full-time. Primary and contributing causes of death are to be recorded in the CRF and the patient's medical record.

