Occupational therapy evaluation ¹⁵		X									X ¹⁴						X ¹⁴
Skin and Oral Biopsies, saliva collection and oral microbiome swabs ¹⁰	--	X	--	--	--	--	--	--		--	X	--	--	--	--	--	--
TBNK	--	X	X		--		--	X			X	--	X	--	X	X ¹⁶	X ¹⁶
Blood for Immunologic Studies (includes PD) ¹¹	--	X	X	--	--	--	--	X			X	--	X	--	X	X	
Blood for PK Studies ¹²	--	X C1D 1	X C1D 15	--	--		--	--X ¹² C4D1	X	--	--	--	--	--	--	--	--

Assessments ¹	Screen (D -28 to -1)	BL BL / C1 D1	C1 D15	C2 D1	C2 D15	C3 D1	C3 D15	12 weeks C4 D1	C4 D15	C5,6 D1	24 weeks C7 D1	C8,9 D1	36 weeks C10 D1	C11, 12 D1	48 weeks C12 D28	Off Treatment ¹³	Optional 3 month follow up ¹³
Visit Window			±5 days	±5 days	±5 days	±5 days	±5 days	±5 days	+/-5 days	± 7 days	± 7 days	± 7 days	± 7 days	± 7 days	± 7 days	± 7 days	± 7 days
Study drug dispensation/ return/accountability	--	X	--	X		X		X		X	X	X	X	X	X	X	--

- 1 Clinic visits can occur ± 5 days. All procedures at protocol-driven time points are performed at the NIH Clinical Center, but if circumstances make this impossible, these data points will be collected in collaboration with referring physicians.
- 2 Baricitinib at assigned doses for 6 months; another 6-month course of treatment will be allowed for patients with response. Only patients who continue therapy beyond 6 months will be required to have clinical monitoring tests during cycles 7 through 12.
- 3 Use NIH diagnostic criteria for cGVHD ([Appendix B](#) and [Appendix M](#): cGVHD New Patient Data Form). In addition, use [Appendix C](#) for clinical differentiation of acute versus cGVHD.
- 4 Chest CT done at screening; a chest CT may be done at response assessments if clinically indicated; a MRI may be done at baseline if clinically indicated
- 5 Pregnancy tests for females of childbearing potential. A female of childbearing potential (FCBP) is a sexually mature female who: 1) has not undergone a hysterectomy or bilateral oophorectomy; or 2) has not been naturally postmenopausal for at least 24 consecutive months (i.e., has had menses at any time in the preceding 24 consecutive months).
- 6 ECG at indicated intervals screening and as clinically indicated. Prolongation of QTc > 0.5 s or QTc interval increases from baseline > 0.06 s is considered as a safety concern.
- 7 Serologies for HIV, HBV, HCV, CMV PCR, blood and urine cultures, respiratory viral panel, CMV PCR. Cultures with no growth present at 48 hours will be deemed negative. BK virus PCR (urine) will be performed at baseline.

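### The 48-week immunosuppression-reduction rate has no stated denominator and no scheduled dose assessment near week 48 for patients off baricitinib by week 24

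*Combined protocol and SAP*

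**What the plan says.** **Endpoint.** Item 3 of the secondary assessments in Section 6.3.2.2 is "Rate of >50% reduction of immunosuppressive therapy at 24 weeks and 48 weeks", with on-study steroid pulses excluded. No denominator is given, and nothing says how a patient who has stopped drug is counted. Section 6.3.1 defines evaluability only for toxicity and for the primary efficacy endpoint. Section 10 does not cover secondary endpoints.

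**When doses are recorded.** Section 6.3.2.3, headed "Other endpoints to be recorded at the evaluation time points", includes steroid doses and doses of other immunosuppressants.

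**Who has a visit at week 48.** Footnote 2 of the Study Calendar (Section 3.7) says: "Only patients who continue therapy beyond 6 months will be required to have clinical monitoring tests during cycles 7 through 12".

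**Who may continue past week 24.** Three places state this:
- Précis: "Patients will have the option to continue baricitinib for an additional 6 months as tolerated if they have stable or responding disease".
- Section 3.1: "patients who have unchanged or responding disease will have the option to continue baricitinib for an additional 6 months as tolerated".
- Section 3.7, footnote 2: "another 6-month course of treatment will be allowed for patients with response".

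**Contacts after stopping.** Section 3.5 provides off-treatment assessments within 30 days for early stoppers (at the last scheduled visit for those who complete 24 or 48 weeks), adverse-event follow-up by phone for at least 30 days, and a 3-month visit that becomes a call if declined. Later calls come "at 12, 18 and 24 months after completing baricitinib". The item on treatment in those calls is "b) ongoing systemic treatment for cGVHD and date of discontinuation".

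**The concern.** The endpoint is fixed at 48 weeks from the start of treatment, but the follow-up clock for anyone off drug starts at the last dose. The two line up at week 48 only for patients still taking baricitinib. Those patients are selected: continuation depends on disease status at week 24, and Section 3.9.1 takes patients off therapy when progression requires a new systemic line. The patients most likely to need more immunosuppression are therefore the ones without a week-48 visit.

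If the rate is reported among patients with week-48 data, it will read as a result for the treated population while describing a subset. The trial has one arm and permits steroid taper from week 4 (Section 4.1), so readers will look to this endpoint for durable steroid-sparing. Section 1.2.2 also cites a retrospective ruxolitinib survey in which an 85% response rate in cGVHD was defined by a 50% decrease in immunosuppression. A rate from selected continuers would invite an uneven comparison with that figure.

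**Working it through.** The plan gives no figure for this endpoint. The power statement in Section 10 concerns the primary response rate and does not enter here.

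**1. Contact times.** Inputs are from Section 3.5. One month = 52.18/12 = 4.35 weeks, so 3 months = 13.0 weeks and 12 months = 52.2 weeks; 30 days = 4.3 weeks. Contact week = stop week + interval.

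| Stop week | 30-day contact | 3-month contact | 12-month call | Smallest distance to week 48 |
|---|---|---|---|---|
| 1 | 5.3 | 14.0 | 53.2 | 5.2 weeks |
| 4 | 8.3 | 17.0 | 56.2 | 8.2 weeks |
| 12 | 16.3 | 25.0 | 64.2 | 16.2 weeks |
| 18 | 22.3 | 31.0 | 70.2 | 17.0 weeks |
| 24 | 28.3 | 37.0 | 76.2 | 11.0 weeks |

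For a patient who completes 24 weeks and stops, the off-treatment assessments are done at the week-24 visit, and the week-28 contact is the 30-day adverse-event follow-up.

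For any stop from week 1 to week 24, the 3-month contact falls at weeks 14–37 and the 12-month call at weeks 53–76. None falls within 4 weeks of week 48. Between the two lies 52.2 − 13.0, or about 39 weeks, with no scheduled contact.

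**2. Content of the calls.** The listed items give treatment ongoing (yes or no) and a stop date.
- All systemic treatment stopped before week 48: the stop date, obtained at the 12-month call, shows it. This counts as a reduction of more than 50%.
- Treatment ongoing at a lower dose: no dose is listed, so the percentage reduction cannot be derived.

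**3. Effect on the rate.** The documents give no expected continuation rate or success rate, so these counts are assumptions: 21 treated, 8 or 14 continuing past week 24, half of those achieving the reduction. Let c = number continuing and k = number of those achieving.
- Observed rate = k/c.
- Lower bound over all treated (no stopper achieves) = k/21.
- Upper bound (every stopper achieves) = (k + 21 − c)/21.

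| c | k | Observed | Lower bound | Upper bound |
|---|---|---|---|---|
| 8 | 4 | 4/8 = 50% | 4/21 = 19% | (4 + 13)/21 = 17/21 = 81% |
| 14 | 7 | 7/14 = 50% | 7/21 = 33% | (7 + 7)/21 = 14/21 = 67% |

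The same observed 50% fits an all-treated rate anywhere in a band 62 percentage points wide (8 continuing) or 33 points wide (14 continuing).

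**The case against.** **General recording rules.** Section 4 requires every therapy taken during the study to be entered on the CRF, the calendar row for cGVHD therapies runs for the whole study, and Section 3.9.2 ends participation only after 2 years of follow-up. Appendix H makes prednisone dose a data element. Calls may go to the primary physician's office, and Section 3.5 describes what the call focuses on without saying that the list is exclusive. A dated dose history could be assembled. This stands as a possibility. But none of these rules sets a contact near week 48 or requires doses after treatment ends, and Appendix H names a dose only for prednisone among concomitant treatments.

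**Computability.** A reader might infer that the 48-week rate can be computed only in patients who continued. The documents do not support that. With stoppers counted as not achieved, a rate over all treated patients is available today, and full cessation can be dated later. The gap is that the plan chooses no rule.

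**Strength of selection.** A reader might also infer that the week-48 group contains only patients who had not failed by week 24. Under the précis and Section 3.1, patients with unchanged disease may continue, and Section 6.3.2.1 classes unchanged disease as lack of response. Only footnote 2 restricts continuation to responders.

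**Importance.** This is one of ten secondary assessments, with no hypothesis attached, and steroid-sparing is not among the objectives in Section 1.1. The 24-week rate in the same line also checks steroid-sparing and is aligned in time with the primary endpoint. A rate among patients still on drug is a legitimate description if labelled as such. All of this stands and limits the point to the 48-week rate.

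**Conclusion.** The point holds in a limited form. For patients off baricitinib by week 24, no scheduled contact falls within 4 weeks of week 48, the listed call items do not capture dose, and Section 6.3.2.2 gives neither a denominator nor a rule for stoppers. Reported by default among patients with data, the 48-week rate would describe a group selected on stable, unchanged or responding disease, or on response alone, depending on which of the three continuation statements is applied.

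The timing finding follows directly from the protocol. The size of any distortion does not: 50% observed against 19–81% or 33–67% over all treated rests on assumed counts. Continuation is optional, so a good responder may decline it, and the bounds run in both directions. A reader should not infer that the all-treated rate must be lower, only that the observed rate says little about it. No defect is claimed in the 24-week rate for patients who reach that visit on drug.

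**What to change.** 1. **Section 3.5 and the Study Calendar:** add one telephone contact at 48 weeks from first dose for every treated patient who is off drug. Record the prednisone-equivalent dose and each systemic immunosuppressant with its dose. At minimum, require a dated dose history at the existing 3- and 12-month contacts; for a week-24 stop, the 12-month call would then look back about 76 − 48 = 28 weeks.
2. **Section 6.3.2.2:** report the 48-week rate over all treated patients, with death or a new systemic cGVHD therapy before week 48 counted as not achieved. Give the number with unknown dose. Label any rate restricted to patients on drug as such. State how a reduction is calculated when a patient takes more than one agent.
3. **Précis, Section 3.1 and Section 3.7 footnote 2:** reconcile the three statements of who may continue past week 24, because they define the group with week-48 visits.

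The cost is at most one short call per patient, under an accrual ceiling of 31, and a few CRF fields. The reported 48-week rate may be less favourable than one restricted to patients still on drug.
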